9. TREATMENT OF SUBJECTS

9.1. Study Drug

Lurasidone 80 mg will be provided as the commercially available oral tablet formulation (Latuda[®]).

Lurasidone and placebo for injection will be supplied as defined in Section 8.2.

Subjects will receive oral lurasidone 80 mg on Days -7 and -6, and be monitored for 5 days to ensure the subject is able to tolerate lurasidone (ie, absence of moderate adverse events).

Subjects who tolerate dosing with oral lurasidone 80 mg will receive lurasidone or placebo injection on Day 1.

9.2. Dose Escalation/Safety Cohort Review

After each cohort, a review of safety data (eg, AE [including potential psychotic symptoms and behavior], vital signs, laboratory data, standard 12-lead ECG, etc.) and lurasidone injectable suspension exposure data for all subjects (or at least 5 lurasidone and 1 placebo subjects completed) in each cohort will be performed. Subsequent dosing at the next dose level/cohort will not occur until safety and exposure data (from at least 14 days after the single lurasidone injectable suspension dose) have been evaluated by the Safety Review Team (SRT). The SRT consists of the PI, the Sponsor's Responsible Physician or designee, the Sponsor's Project Medical Lead, the Sponsor's Head of Translational Medicine and Early Development team or designee and the Medical Monitor. The SRT will also determine if sentinel subject dosing is required for study cohorts after Cohort 1.

The decision to proceed to the next dose level/cohort and at what dose level will also be made by the voting members of the SRT, based on a review of the clinical observations, laboratory data, and exposure data, and will require a majority agreement concerning acceptable safety and tolerability of lurasidone injectable suspension. Based on these safety reviews, a more conservative dose escalation may be used that will be less than the planned dose escalation, or subsequent cohorts may repeat a dose level or de-escalate. For each cohort, the SRT will monitor and review AE and exposure data 14 days and 28 days after the injection dose.

Treatment assignments for a particular cohort may be unblinded during a safety review meeting, but only after a blinded review of the safety data has been completed. PK exposure data will be utilized in the safety review; thus, it will be necessary for the bioanalytical laboratory to be unblinded to treatment assignment for the subjects.

9.3. Determination of the MID and MTD

The MID will be defined as the dose of Lurasidone injectable suspension at which dose limiting toxicity (DLT) occurs. Dose-limiting toxicity is indicated by the occurrence of intolerable AEs, which are not fully defined a priori, but will be determined from the study data at the SRT meetings. The following criteria will be used as a guide:

- If 50% or more of the subjects receiving study drug have either multiple moderate AEs and/or a severe AE possibly related to study drug as determined by the SRT MID may have been reached, and safety data will be unblinded.
- If more than one subject but less than 50% of the subjects receiving study drug have either multiple moderate AEs and/or a severe AE possibly related to study drug as determined by the SRT a dose level/cohort may be repeated or a modified escalation may be employed, and safety data of the subject(s) in question will be unblinded.

The SRT may decide to stop dose escalation, repeat a dose, or de-escalate if the number, severity, or type of AEs indicates that higher doses would not be tolerated. In addition, the following stopping criteria for dose-escalation will also be used to assess whether to proceed to a higher dose level in the next cohort. Dose escalation will not occur, although a dose cohort may be repeated or de-escalate if any of the following criteria are met:

• Adverse Events

A SAE associated with the use of the study drug with a reasonable possibility that
the event may have been caused by the study drug occurs in any subject on
active drug.

• Cardiac Parameters

A confirmed value of QTcF interval > 500 ms or > 60 ms change from baseline,
 based on cardiologist over read ECGs occurs in any 2 subjects on active drug.

• Hepatic Parameters

- Liver function tests (alanine aminotransferase [ALT], aspartate aminotransferase [AST], or total bilirubin [TBL]) > 3 x upper limit of normal (ULN) occurs in any 3 subjects on active drug.
- Any one of Hy's law criteria are met for any subject on active drug.
- ALT or AST $> 8 \times ULN$.
- ALT or AST > 5 x ULN for more than 2 weeks.
- ALT or AST > 3 x ULN and (TBL > 2 x ULN or international normalized ratio [INR] > 1.5).
- ALT or AST > 3 x ULN with the appearance of fatigue, nausea, vomiting, right upper quadrant pain or tenderness, fever, rash, and/or eosinophilia (> 5%).

• Injection site reactions will be assessed for severity according to each of the following categories (per the Investigator's judgement):

Local Reaction to Injectable Product	Mild (Grade 1)	Moderate (Grade 2)	Severe (Grade 3)	Potentially Life Threatening (Grade 4)
Pain	Does not interfere with activity	Repeated use of non-narcotic pain reliever > 24 hours or interferes with activity	Any use of narcotic pain reliever or prevents daily activity	Emergency room (ER) visit or hospitalization
Tenderness	Mild discomfort to touch	Discomfort with movement	Significant discomfort at rest	ER visit or hospitalization
Erythema/Redness	2.5 – 5 cm	5.1 – 10 cm	> 10 cm	Necrosis or exfoliative dermatitis
Induration/Swelling	2.5 – 5 cm and does not interfere with activity	5.1 – 10 cm or interferes with activity	> 10 cm or prevents daily activity	Necrosis

Reference: FDA Guidance for Industry "Toxicity Grading Scale for Healthy Adult and Adolescent Volunteers Enrolled in Preventive Vaccine Clinical Trials," 2007.

Adverse events, including SAEs, which start prior to study drug injection, will not be considered for stopping criteria.

Once a safety stopping criterion is reached, the study will not escalate beyond that dose level. If none of the stopping criterion has been attained, the study will proceed to the next higher dose level. Dosing of an additional cohort or cohorts at a dose between the identified MID and the highest dose below the MID may be conducted. The highest tolerated dose below the MID will be defined as the MTD for a single lurasidone injectable suspension dose.

If the MTD is not established, additional dose cohorts may be commenced until the MTD is reached.

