2. LIST OF ABBREVIATIONS AND DEFINITIONS OF TERMS

The abbreviations and the definition of key study terms used in the clinical study protocol are shown in Table 3 and Table 4.

Table 3: List of Abbreviations

Abbreviation	Full Form
AE	Adverse event
ALT	Alanine aminotransferase
AST	Aspartate aminotransferase
ATC	Anatomical Therapeutic Chemical
BMI	Body mass index
CFR	Code of Federal Regulations
CI	Confidence Interval
CLIA	Clinical Laboratory Improvement Amendments
CRF	Case report form (or electronic case report form)
CRO	Contract research organization
C-SSRS	Columbia-Suicide Severity Rating Scale
CV	Coefficient of variation
ECG	Electrocardiogram
EDC	Electronic data capture
EPS	Extrapyramidal symptoms
FDA	U.S. Food and Drug Administration
GCP	Good Clinical Practice
hCG	Human chorionic gonadotropin
ICF	Informed consent form
ICH	International Council on Harmonisation
IEC	Independent Ethics Committee
IND	Investigational New Drug
IPD	Important protocol deviation
IRB	Institutional Review Board
IUD	Intrauterine device
IXRS	Interactive Voice/Web-based Response System
MedDRA	Medical Dictionary for Regulatory Activities

Table 3: List of Abbreviations (continued)

Abbreviation	Full Form
MMRM	Mixed model for repeated measures
PANSS	Positive and Negative Syndrome Scale
PK	Pharmacokinetic(s)
PR	Time between P wave and QRS in electrocardiography
PT	Preferred term
PVG	Pharmacovigilance
QRS	Electrocardiographic wave (complex or interval)
QT	Electrocardiographic interval from the beginning of the QRS complex to the end of the T wave
QTc	QT interval corrected for heart rate
SAE	Serious adverse event
SAP	Statistical analysis plan
SOC	System organ class
SOP	Standard Operating Procedure
SRT	Safety review team
US	United States

Table 4: Definition of Key Study Terms

Terms	Definition of terms
CRF	A printed, optical, or electronic document designed to record all of the protocol required information to report to the Sponsor for each study subject.
Screened Subject	Any subject who signed the study specific informed consent and completed at least one study related procedure.
Screen Failures	Any subject who signed the study specific informed consent but either failed to meet study requirements during screening or met study requirements at screening but was not enrolled/randomized.
Study Drug (or Study medication)	Term to cover investigational drug, placebo, and/or active control.
Treatment Period	The period of the study in which the study drug is administered.

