6.2. Treatment Assignment and Blinding

6.2.1. Treatment Assignment

The treatment schedule will be generated by a non-study biostatistician.

For each cohort, the randomization number will be sequentially assigned as subjects qualify for the study. Once 8 subjects per cohort are dosed, alternate subjects who are not needed to complete enrollment of a cohort will be discharged following reintroduction of their prior medication if they are clinically stable (in the Investigator's opinion).

Once a randomization number has been assigned, it cannot be reused.

Prior to dosing, all eligible subjects will be given a randomization number that assigns them to one of the two treatments. Randomization numbers will be assigned sequentially in the order the subject became eligible to participate in the study. The treatment schedule, a list consisting of the randomization numbers and their corresponding treatment assignment will be generated according to appropriate standard operating procedure(s).

Subjects will receive single oral lurasidone 80 mg doses on Days -7 and -6, and be monitored for 5 days to ensure the subject is able to tolerate lurasidone (ie, absence of moderate adverse

events). Subjects who tolerate dosing with oral lurasidone 80 mg will be eligible for randomization on Day 1.

The study is planned to include up to 5 cohorts. A total of 8 subjects (6 active and 2 placebo) will be dosed in each cohort. Lurasidone injectable suspension dosing will be initiated at 30 mg given as an intramuscular (IM) injection at the ventrogluteal site. Subsequent cohorts are planned to be dosed at 75, 150, 300, and 450 mg IM at the ventrogluteal site. Dose strengths after the first dose level may be modified based on safety assessments and exposure to lurasidone injectable suspension.

All 5 planned dose cohorts may not be used, depending on the dose escalation strategy employed. Additional cohorts may be included in this study, as necessary, and determined following a review of safety and exposure of lurasidone injectable suspension. Planned dose levels may be modified or repeated based on the overall safety profile of the current and/or previous cohorts.

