6.2.2. Blinding

This is a double-blind study.

All study drug (active or placebo) will be dispensed according to the randomization schedule supplied by the Sponsor or its representative, using a method that will assure that subjects and blinded study site personnel remain blinded to the treatment (ie, active or placebo) being administered.

Provided doses will be clearly labeled with a unique subject identifier and verified during preparation and at the time of administration to mitigate any possibility of dosing/randomization error.

During the conduct of the cohorts, in order to maintain the blind during the time of study drug administration, up until a safety review of AEs and other safety data for a cohort is conducted, an unblinded clinical site pharmacist/nurse will dispense study drug in a manner that will protect the blind upon administration. All study drug (lurasidone injectable suspension or placebo) will be dispensed according to the randomization schedule supplied by the Sponsor or its representative, using a written study drug dispensing procedure that will assure that subjects remain blinded to the treatment being administered.

Subjects, Investigator staff, persons performing the assessments, clinical operations personnel, data analysts, and personnel at clinical laboratories will remain blind to the identity of the treatment from the time of randomization until database lock and unblinding, with the exception

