14.2. Analysis Populations

Three analysis populations will be defined:

- Safety population: The Safety population will consist of all subjects who were randomized and received study drug. All analyses will be performed according to treatment received. This population will be used for analysis of baseline and safety data.
- Pharmacokinetic (PK) population: The PK population includes Safety population subjects who received lurasidone injectable suspension (active) and have at least 1 postdose quantifiable serum or urine lurasidone injectable suspension and metabolite(s) concentration. This population will be used for PK analysis.
- Pharmacodynamic (PD) population: The PD population will include all subjects in the Safety Population who have valid baseline and at least one post-baseline PANSS assessment.

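### The 50% guide for the minimum intolerable dose counts placebo subjects, and no step reapplies it to active subjects once assignments are known (minor)

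*Protocol*

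**What the plan says.** Protocol 9.3 gives two guide bullets for judging the MID. The upper one begins "If 50% or more of the subjects receiving study drug have either multiple moderate AEs and/or a severe AE possibly related to study drug". When it is met, the MID may have been reached and the safety data are unblinded. The lower one covers more than one subject but under 50% of the same denominator. It allows a repeated dose level or a modified escalation, and "safety data of the subject(s) in question will be unblinded".

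Three places fix what study drug means:

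- Table 4 defines it as "Term to cover investigational drug, placebo, and/or active control".
- Section 6.2.2 states "All study drug (active or placebo) will be dispensed according to the randomization schedule supplied by the Sponsor or its representative".
- Section 14.2 states "The Safety population will consist of all subjects who were randomized and received study drug", and that population includes the pooled placebo group.

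On cohort size, Section 6.2.1 states "A total of 8 subjects (6 active and 2 placebo) will be dosed in each cohort".

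Other criteria in 9.3 count differently. The QTcF stop applies when the finding "occurs in any 2 subjects on active drug". The SAE, three-subject liver-test and Hy's law criteria are likewise limited to active drug.

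Section 9.2 allows assignments to be unblinded at a review meeting, "but only after a blinded review of the safety data has been completed". Neither 9.2, 9.3 nor SAP 5.1 tells the SRT to recalculate the percentage among active subjects afterwards.

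**The concern.** Determining the MID and the maximum tolerated dose (MTD) is a stated aim (Protocol 6.1), and 9.3 defines the MTD as the highest tolerated dose below the MID. The tier that a cohort falls into therefore bears on a reported result. With two placebo subjects in the denominator and no placebo event, a dose that affects exactly half of the exposed subjects falls short of the 50% mark.

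This is most likely when placebo subjects rarely qualify. Local reactions may be such a case. Section 6.3.2 reports granuloma as the primary finding in the dog, with no no-observed-adverse-effect level. Section 9.3 grades injection-site reactions but gives no number of affected subjects that would halt escalation. That such reactions would be mostly drug-related, and so rare on placebo, is an inference; the documents give no rates.

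**Working it through.** **Inputs.** Cohort of 6 active and 2 placebo, up to 5 cohorts (6.2.1). Upper tier: at least 50%. Lower tier: more than one subject but under 50% (9.3). Minimum review set: 5 active and 1 placebo (9.2). Event rates are assumptions.

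**The plan's own figures.** 6 + 2 = 8 per cohort and 5 × 8 = 40 in total, as stated. As worded, 50% of 8 is 4 subjects. Among active subjects only, 50% of 6 is 3.

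**Tier by count, full cohort, no placebo event**

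| Active affected | As worded (of 8) | Active only (of 6) |
|---|---|---|
| 2 | 25.0%, lower | 33.3%, lower |
| 3 | 37.5%, lower | 50.0%, upper |
| 4 | 50.0%, upper | 66.7%, upper |

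Only the count of 3 differs.

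**All outcomes.** There are 7 × 3 = 21 combinations (0–6 active, 0–2 placebo). The tier differs in five:

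- 3 active + 0 placebo: lower as worded, upper among active. This is the only miss in the unsafe direction.
- 2 + 2: 4/8 = 50%, upper as worded; 2/6 = 33%, lower among active.
- 1 + 1, 0 + 2 and 1 + 2: lower as worded; no tier among active, because at most one active subject is affected.

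**Minimum review set (5 + 1).** Three affected active subjects give 3/6 = 50% as worded and 3/5 = 60% among active, both upper. No count differs when the placebo subject is unaffected.

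**How often the 3 + 0 outcome occurs.** With active rate p, placebo rate q and independent subjects, P(3,0) = 20 p³(1−p)³ × (1−q)².

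- p = q = 0.1: 20 × 0.001 × 0.729 × 0.81 = 0.012
- p = q = 0.2: 20 × 0.008 × 0.512 × 0.64 = 0.052
- p = 1/2, q = 0: 20/64 = 0.31; with q = 0.1 it is 0.25, and with q = 0.2 it is 0.20
- p = 1/3 or 2/3, q = 0: 160/729 = 0.22

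**Chance of an upper-tier reading at q = 0**

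| Active rate | As worded, P(X ≥ 4) | Active only, P(X ≥ 3) |
|---|---|---|
| 1/3 | 0.10 | 0.32 |
| 1/2 | 0.34 | 0.66 |
| 2/3 | 0.68 | 0.90 |

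**What a recount in both directions would do.** The four combinations that would move down (2+2, 1+1, 0+2, 1+2) have total probability 0.074 at 10%/10% and 0.162 at 20%/20%. The one that moves up has 0.012 and 0.052. At low event rates, a two-way recount would lower tiers more often than it raises them.

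**The case against.** The strongest reply is that the pooled wording suits what the bullets do. Each ends in an unblinding action, and a trigger for unblinding has to be countable while the review is blinded, which 9.2 puts first. The criteria limited to active drug are stops on escalation, so the different wording does not by itself show a drafting slip. This stands, and it is why the pooled count should stay. It does not explain why the percentage is left unrevised once assignments are known.

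The second reply is that the missed outcome is largely handled. The lower tier unblinds the three affected subjects, the 6 + 2 split is known, and an attentive SRT would see 3 of 6. Both tiers are permissive, and escalation needs a majority agreement that the product is acceptably tolerated. This also stands and limits the consequence, but the written guide still points the SRT to the lower tier.

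Third, a reader might infer that these bullets are the only check on local toxicity. The documents do not support that. Section 6.3.2 lets escalation go ahead when injection-site findings are absent at two weeks and no other stopping criterion is met. Read literally, three active subjects with local reactions in that time fail the condition whatever their tier. The statement sits in a rationale section and is not repeated in 9.3, but it bears directly on the toxicity most expected.

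**Conclusion.** The point holds as a minor one. As worded, the threshold mislabels one of 21 possible outcomes of a full cohort in the unsafe direction: 3 of 6 active subjects affected with no placebo event reads 37.5% instead of 50%. The denominators and the list of outcomes follow from the documents. The frequencies (1.2%, 5.2% and 31% of cohorts in the three main scenarios) rest on assumed event rates and independent subjects. The 31% is the most favourable case for the concern, since P(3,0) is largest at an active rate of 1/2 with no placebo events.

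A reader might infer that the rule would let an intolerable dose escalate. The documents do not support that: the bullets are a guide, the SRT may stop, repeat or de-escalate on judgement, the affected subjects are unblinded in the lower tier, and 6.3.2 adds its own injection-site condition. What is shown is a wrong tier label, not necessarily a wrong dose decision.

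**What to change.** Keep both pooled bullets and their unblinding actions as the blinded trigger. After them, add to Protocol 9.3:

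*Once the affected subjects are unblinded, the MID may also have been reached if 50% or more of the subjects dosed with active drug in the cohort (3 or more of 6) meet the criterion.*

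Apply the recount upward only, so that no caution raised by the pooled count is withdrawn.

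No new trigger is needed, because three affected subjects already fall in the lower tier and are unblinded. Whole-cohort unblinding need not increase either: in a full cohort the active denominator is 6 by design, so only the affected subjects' assignments are required.

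The cost is a recount at the SRT meeting and somewhat more frequent flags that the MID may have been reached. The increase is the 3 + 0 probability: 1.2% of cohorts at 10%/10%, 5.2% at 20%/20% and 31% at active 1/2 with placebo 0. No subjects or assessments are added.

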Once a safety stopping criterion is reached, the study will be terminated at that dose level. If none of the stopping criteria has been attained, the study will proceed to the next higher dose level. Dosing of an additional cohort or cohorts at a dose between the identified MID and the highest dose below the MID may be conducted. The highest tolerated dose below the MID will be defined as the MTD for a single lurasidone injectable suspension dose.

If the MTD is not established, additional dose cohorts may be commenced until the MTD is reached.

Safety, Pharmacokinetic, and Pharmacodynamic Assessments

Safety will be assessed throughout the study by monitoring AE (including injection site reactions),

Name of Investigational Product: Lurasidone injectable suspension

Name of Active Ingredient: Lurasidone (DSP-1349M)

physical examinations, vital signs (pulse rate, respiration rate, and body temperature), clinical laboratory tests (hematology, serum chemistry, urinalysis, lipid panel, coagulation panel, and thyroid panel), standard 12-lead ECGs, and the Columbia-Suicide Severity Rating Scale (C-SSRS).

Blood samples will be collected for serum PK profiling of lurasidone and its metabolites in serum (ID-14283, ID-14326, ID-11614, ID-20219 and ID-20220) and urine (ID-14283, ID-14326, and ID-11614) in this subject population after injection dosing at the timepoints specified in the Schedule of Assessments (see Table 2). Serum and urine samples collected for PK assessment may also be used for the additional characterization and/or bioanalytical method development of putative metabolites of lurasidone and for biomarker measurement.

The pharmacodynamic impact of lurasidone injectable suspension will be assessed using the Positive and Negative Schizophrenia Symptoms Scale (PANSS).

Number of Subjects (planned):

Approximately 8 subjects will be randomized per cohort for a total of up to 40 subjects and up to 5 cohorts.

Alternate subjects may be admitted to the clinical site in order to ensure that 8 subjects are dosed in each cohort. Subjects who are randomized but not dosed will be replaced by the alternate subject(s).

Once 8 subjects per cohort are dosed, alternate subjects who are not needed to complete enrollment of a cohort will be discharged following reintroduction of their prior medication if they are clinically stable (in the Investigator's opinion).

Main Diagnosis and Criteria for Enrollment

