6.3.2. Rationale for the Dosages

Dosing for the lurasidone injectable suspension formulation is based on the amount in mg of lurasidone present at the injection site following IM administration, which was $\sim\!60$ mg at the lowest dose of 7.5 mg/kg in the dog. There was no no-observed-adverse effect level determined in the dog; therefore a 2-fold reduction in the amount of lurasidone at the injection site was recommended, which is equal to 30 mg. At the clinical formulation's fixed concentration of 150 mg/mL, this dose will be an injection volume of 0.2 mL.

A 2-fold reduction is considered appropriate because the primary finding of granuloma is common following IM administration of an irritating substance. Clinicians are familiar with appropriate monitoring. This finding is reversible and non-lethal. The pharmacology of lurasidone is well known, and systemic findings in humans have been characterized over a range of serum concentrations.

After the lurasidone injectable suspension starting dose of 30 mg, dose escalation will be as follows: 75, 150, 300, 450 mg for a single IM injection. A 6 week monitoring period for adverse events will be employed in this study. In animals, the injection site findings were apparent within 1 week and findings persisted for an additional week before beginning to resolve. Therefore, if no injection site findings are seen within 2 weeks and no other stopping criteria are met, dose escalation may proceed.

Projection of PK following each cohort indicates that C_{max} will not exceed 348 ng/mL. This value is the C_{max} at 400 mg orally, which is the MTD (Study D1050217, Day 6). It is unlikely that IM administration will exceed this concentration as the depot will absorb more slowly than following oral administration. Therefore, routine safety monitoring will be utilized to determine stopping criteria.

In order to ensure subjects who are unable to tolerate lurasidone do not receive the lurasidone injectable suspension formulation, subjects will be evaluated for tolerability after administration of oral lurasidone 80 mg for 2 days (ie, two doses) prior to lurasidone injectable suspension administration.

The oral lurasidone 80 mg dose was previously established as the maximum tolerated dose (MTD) in healthy subjects. In subjects with schizophrenia, an oral lurasidone dose of 400 mg/day was previously established as the MTD.

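### The hepatic stop that needs more than 2 weeks of raised ALT or AST cannot be met at Day 15, the earliest data cut for escalation, so one narrow case rests on the SRT vote alone

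*Protocol*

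**What the plan says.** Protocol Section 9.3 lists hepatic findings that bar escalation. One is "ALT or AST > 5 x ULN for more than 2 weeks". The others carry no duration: ALT or AST above 8 x ULN; above 3 x ULN with bilirubin above 2 x ULN or INR above 1.5; above 3 x ULN with listed symptoms or eosinophilia; and ALT, AST or bilirubin above 3 x ULN in three active subjects. Adverse events "which start prior to study drug injection, will not be considered for stopping criteria".

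Under Section 9.2, escalation to a new level "will not occur until safety and exposure data (from at least 14 days after the single lurasidone injectable suspension dose) have been evaluated"; this task falls to a Safety Review Team (SRT). The decision draws on clinical, laboratory and exposure data and "will require a majority agreement concerning acceptable safety and tolerability of lurasidone injectable suspension". There is a second look: "For each cohort, the SRT will monitor and review AE and exposure data 14 days and 28 days after the injection dose". Section 6.3.2 bases the two-week interval on the timing of injection-site findings in animals and concludes: "Therefore, if no injection site findings are seen within 2 weeks and no other stopping criteria are met, dose escalation may proceed".

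On what follows a stop, Section 9.3 says "Once a safety stopping criterion is reached, the study will not escalate beyond that dose level", and the synopsis says "Once a safety stopping criterion is reached, the study will be terminated at that dose level". Section 9.3 also says that the study moves up a dose level when no stopping criterion has been attained.

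**The concern.** The sponsor wrote this rule to inform the escalation decision, but it cannot operate at the earliest time that decision may be taken. Section 6.3.2 makes escalation depend on no other stopping criterion being met at two weeks. For a subject at Day 15, that is automatically true of this criterion.

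Take an active subject with ALT of 6 x ULN on Days 8 and 15, no symptoms, and normal bilirubin, INR and eosinophils. No hepatic stop is met at the Day 15 review, and the written default is to go on. What would be at stake is a higher dose in a first-in-human study of a slowly dissolving intramuscular depot that cannot be withdrawn once injected. The largest planned step is 2.5-fold (75 / 30 mg).

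**Working it through.** The plan states no figure to reproduce. The check is calendar arithmetic.

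**Inputs.** Injection is on Day 1 and there is no Day 0 (SAP 7.1), so days since injection = Day − 1. The threshold is strictly more than 14 days (Protocol 9.3). The minimum data cut is 14 days after injection (9.2), which is Day 15. Scheduled post-injection chemistry is on Days 8, 15, 22, 29 and 33 and at follow-up (Table 2, footnote d).

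**Step 1: the earliest review.** Longest possible post-injection elevation at Day 15 = 15 − 1 = 14 days. This is not more than 14, so the criterion cannot be met.

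**Step 2: scheduled draws.** Duration shown = later day − day first seen.

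| First seen | Day 15 | Day 22 | Day 29 | Day 33 |
|---|---|---|---|---|
| Day 8 | 7 | 14 (not met) | 21 (met) | 25 |
| Day 15 | – | 7 | 14 (not met) | 18 (met) |

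The delay after the Day 15 cut is 29 − 15 = 14 days or 33 − 15 = 18 days. An elevation first seen on Day 15 is not shown as met at the 28-day SRT review.

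**Step 3: repeat tests.** Section 11.2 permits repeats, Appendix II requires them, and neither gives an interval. Assume repeats every 1 to 5 days after the elevation is first seen. The first test beyond 14 days then falls 15 or 16 days later: Day 23 or 24 (8 + 15, 8 + 16), or Day 30 or 31 (15 + 15, 15 + 16). That is 8 to 9 or 15 to 16 days after the cut. An unscheduled sample before Day 8 could shorten this further.

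**Step 4: when the next cohort would be dosed.** Day 15 is a data cut, not a dosing date. Day −12 to Day 1 is 12 days. If the inpatient run-in starts only after a vote on Day 15, dosing falls on lower-cohort Day 15 + 12 = Day 27. The remaining gap, from daily repeats to scheduled draws only, is:
- first seen Day 8: max(0, 23 − 27) = 0 to 29 − 27 = 2 days;
- first seen Day 15: 30 − 27 = 3 to 33 − 27 = 6 days.

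With dosing on Day 29 the gap is 0 days (first seen Day 8) or 30 − 29 = 1 to 33 − 29 = 4 days (first seen Day 15). From Day 33 it is closed.

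**Step 5: the uncovered pattern.** The hepatic stops without a duration remove values above 8 x ULN, values with raised bilirubin or INR, values with symptoms or eosinophilia, and three or more affected active subjects. What remains is one or two active subjects with an isolated, asymptomatic value above 5 and up to 8 x ULN. Section 9.3 also refers to any one of Hy's law criteria. Reading that as ALT above 3 x ULN alone would make the three-subject, 5 x and 8 x rules redundant, so it does not fill this space.

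**The case against.** The best defence is that this is the design. Section 9.3 adds the numeric stops to SRT discretion rather than replacing it. The SRT may stop, repeat or de-escalate on the number, severity or type of events, and escalation needs a positive majority with laboratory data on the table. A clinically significant ALT of 6 x ULN is recorded as an adverse event and followed (11.2), and the sponsor must be told (10.2). A persistence rule that has not matured at a minimum interval is no contradiction: 14 days is a floor, and the rule continues to apply afterwards. Subjects dosed earlier have longer follow-up. The Cohort 1 sentinel pair would be at about Day 22 when the last subject reaches Day 15, although a sentinel first raised on Day 8 would then show only 14 days. All of this stands. It makes the case narrow and the interval short.

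Three stronger readings are tempting, and the documents do not support them.
- *Such a subject would go unnoticed.* The SRT would see the value at the Day 15 review. What is missing is a rule that binds its vote.
- *Nothing governs a higher cohort already open when a lower one meets the criterion late.* The no-escalation sentence in 9.3 and its synopsis counterpart are tied to no meeting date. Read plainly, they bar a higher dose for anyone not yet injected. Section 13 also lets the investigator, after consulting the sponsor, end part or all of the study.
- *The 28-day review leaves out laboratory findings because it names only adverse event and exposure data.* Section 11.2 brings clinically significant laboratory abnormalities in as adverse events.

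The defence does not supply a firm stop at the Day 15 review. Nor does it give specific text on the rest of a partly dosed higher cohort or on setting the MID and MTD in that sequence.

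**Conclusion.** The timing point is exact: for a subject at Day 15 the criterion cannot be met, and on scheduled draws it is first shown 14 or 18 days after that cut. The consequence is limited. It concerns one or two active subjects with isolated, asymptomatic values above 5 and up to 8 x ULN, for whom the SRT vote is the only barrier. The practical gap is 0 to 6 days if the next cohort would be dosed on about Day 27. It is up to 18 days only if dosing could follow immediately on the Day 15 cut, which is unlikely because exposure data and a vote are needed first. The shorter range assumes that the run-in waits for the vote, which no text requires, and the repeat-test figures assume an interval of 1 to 5 days.

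This is an inexpensive improvement that should be made. It does not show that the escalation scheme is unsafe or self-contradictory.

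**What to change.** Amend Sections 9.2 and 9.3 to say:

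1. The next higher level is not dosed while any active subject has ALT or AST above 5 x ULN unresolved at the 14-day review. Section 9.2 already allows unblinding at that meeting once the blinded review is done, so active subjects can be identified.
2. The test is repeated, at a stated interval, until the value is 5 x ULN or below or the criterion is met. This also settles the difference between 11.2 and Appendix II for this finding.
3. If a lower cohort meets a criterion after a higher cohort has begun dosing, further dosing there pauses for SRT review, and the SRT resets the MID and MTD on the lower cohort's data.

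This needs amendment wording and no new scheduled visits. Extra draws fall only on an affected subject. Only when triggered, the next cohort waits at most about 8 to 18 days beyond the earliest data cut, or 0 to 6 days if it would otherwise be dosed on about Day 27. The real trade-off is that a fixed hold replaces SRT discretion for this one finding, so a transient elevation could delay a cohort.
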